During exercise, plasma glucose increased slightly with Glucagon RTU compared to a decrease with control and insulin reduction, and a greater increase with glucose tablets. Insulin levels were not different among sessions, while glucagon increased with Glucagon RTU. Hypoglycemia (≤ 70 mg/dL (3.89 mmol/L)) was experienced by 6 subjects in the control arm, 5 subjects in the insulin reduction arm, and no subjects using glucose tablets or Glucagon RTU. A total of 5 subjects experienced hyperglycemia (≥ 250 mg/dL) with glucose tablets and 1 with Glucagon RTU.

There were no SAEs reported in the study and no subjects discontinued prematurely. No participant reported nausea during exercise, but 2 participants reported nausea with symptoms of bloating post-exercise after receiving Glucagon RTU.

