12.4.2. Analysis of the Primary Efficacy Endpoint(s)

The primary efficacy analysis will be analyzed by ANOVA comparing the mean incidence rate among the 3 treatment groups. All statistical significance testing will be 2-sided with a p-value <0.05 . Efficacy endpoints will be analyzed using the ITT and PP analysis populations. After performing the F-test and if an overall $p<0.05$ is achieved, post-hoc analysis of group means will be conducted to statistically determine which group means differ.

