### 1.3 DETERMINATION OF SAMPLE SIZE

The primary endpoint of the study is the incidence of hypoglycemia (glucose  $\leq$  70 mg/dL (3.89 mmol/L)) associated with an exercise session, which occurred within the 12-week outpatient follow-up, as measured by BGM. The null hypothesis is that there is no difference between the treatment groups in the incidence of exercise-associated hypoglycemia, and the alternative is there is a difference between the treatment groups in terms of the incidence of exercise-associated hypoglycemia. With an effect size estimate of 0.262 (variance of means 59, common standard deviation 15), 80% power and an alpha of 0.05, using a one-way analysis of variance, 14 subjects per treatment group in the Outpatient Stage is required. Accounting for 15% attrition, a total of 48 subjects will be randomized.

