#### **4.3.6 Primary Endpoint Analysis:**

The primary efficacy hypothesis test for the study is as follows:

Null Hypothesis: There is no difference between the treatment groups in the mean incidence of hypoglycemia (glucose  $\leq 70$  mg/dL (3.89 mmol/L)) associated with an exercise session occurring within the 12 weeks of out-patient treatment as measured by BGM.

Alternative Hypothesis: There is a difference between treatment groups in the mean incidence of hypoglycemia (glucose  $\leq 70$  mg/dL (3.89 mmol/L)) associated with an exercise session occurring within the 12 weeks of out-patient treatment as measured by BGM.

Incidence rate per subject is calculated by summing the number of exercise sessions completed within 12 weeks and dividing this denominator by the number of hypoglycemic events that

occurred during those exercise sessions (Incidence Rate = number of exercise sessions / inter/post-exercise hypoglycemic events). Events associated with an exercise session are defined as hypoglycemic events that occur during or within 30 minutes of exercise completion.

The primary efficacy analysis will be analyzed by ANOVA comparing the mean incidence rate between the three treatment groups. All statistical significance testing will be two-sided with a p-value  $<0.05$ . Efficacy endpoints will be analyzed using the ITT and PP analysis populations for Outpatient phase, if performed F-test yields an overall p-value less than 0.05 ( $p<0.05$ ), post-hoc analysis of groups means will be conducted to statistically determine which group means differ.

Parameters that do not meet normality criterion will be analyzed non-parametrically. Overall treatment effect will be assessed using Friedman's test. If the overall treatment effect is significant in the Friedman's test, pairwise treatment comparisons will be assessed using the following tests.

- If the difference between two treatments is normally distributed (i.e., the p-value is  $\geq 0.05$  for Shapiro-Wilk test, the Tukey Test will be used.
- If the difference between two treatments is not normally distributed and the distribution is highly skewed, then the sign test/Kruskal Wallis test will be used.

Example of SAS syntax code that can be used for primary endpoint analysis is provided in APPENDIX 1.

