### **4.6 APPENDICES**

#### **4.6.1 APPENDIX 1. Example of SAS syntax code for primary endpoint analysis.**

The following SAS syntax code can be referred to during programming of primary endpoint analysis:

```
PROC ANOVA DATA = clover;
  CLASS trt_o;
  MODEL param = trt_o;
RUN;
```

Alternative:

```
PROC GLM DATA = xx;
  CLASS trt_o;
  MODEL param = trt_o/ ss3;
  LSMEANS trt_o / PDIFF CL ALPHA=0.05;
RUN;
```

Alternative:

```
PROC MIXED DATA=school METHOD=type3;
  CLASS trt_o;
  MODEL param= trt_o;
RUN;
```

The following SAS syntax example code can be referred to during testing the normality of the residuals using the Shapiro-Wilk W-test.

```
PROC UNIVARIATE DATA=xxxxx NORMAL PLOT;
  VAR yyyy;
  QQPLOT yyyy /NORMAL (MU=EST SIGMA=EST COLOR=RED L=1);
RUN;
```

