#### 4.6.3 APPENDIX 3. Example of SAS syntax code for exploratory analysis.

The ANCOVA model can be analyzed using the following SAS code example:

```
PROC MIXED DATA=XXXX;
  CLASS SUBJECT TREATMENT trtSEQ sex;
  MODEL &par= TREATMENT trtSEQ sex age weight/DDFM=SATTERTH;
  RANDOM SUBJECT (SEQ);
  REPEATED / GROUP=TREATMENT SUB=SUBJECT R;
  LSMEANS TREATMENT / CL;
  LSMESTIMATE TREATMENT 'Treatment A vs. Treatment B' 1 1 0 /
  CL ALPHA=0.025 E LOWER;
RUN;
```

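### The primary ANOVA pools one variance over three arms and plans nothing for unequal variances; if glucagon shrinks the spread as well as the rate, unadjusted 95% intervals against control can cover as little as about 88%

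*SAP*

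**What the plan says.** The sample size (SAP 1.3, same figures in Protocol 12.2) uses an "effect size estimate of 0.262 (variance of means 59, common standard deviation 15), 80% power and an alpha of 0.05" in a one-way ANOVA and concludes that "14 subjects per treatment group in the Outpatient Stage is required". One SD serves all three arms.

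The analysis follows the same model. SAP 4.3.6: "The primary efficacy analysis will be analyzed by ANOVA comparing the mean incidence rate between the three treatment groups". If the overall F-test is significant, Protocol 12.4.2 adds that "post-hoc analysis of group means will be conducted to statistically determine which group means differ"; SAP 4.3.6 says the same. Neither names a pairwise method for this branch. SAP Appendix 1 offers three alternative examples (PROC ANOVA, PROC GLM, PROC MIXED), each with a single residual variance. Only the GLM example produces pairwise intervals, with "LSMEANS trt_o / PDIFF CL ALPHA=0.05" and no multiplicity adjustment.

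The only assumption checked is normality. Where it fails, SAP 4.3.6 moves to Friedman's test, followed by Tukey or sign/Kruskal-Wallis comparisons. Nothing addresses equality of variances for the primary endpoint. The SAP does allow arm-specific variances elsewhere: the exploratory code in Appendix 3 contains "REPEATED / GROUP=TREATMENT SUB=SUBJECT R".

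**The concern.** The outcome is a per-subject rate that cannot fall below zero. An arm whose rate is pushed towards zero will usually have less spread than the control arm. The pilot described in Protocol 4.2, with 15 subjects, makes low rates on glucagon plausible: hypoglycemia occurred in "5 subjects in the insulin reduction arm, and no subjects using glucose tablets or Glucagon RTU".

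If both glucagon arms are tight and control is not, the pooled variance lies below the control arm's variance, and the standard error for glucagon versus control is too small. If only one glucagon arm works, its small variance drags the pooled value down for the comparison of the other two arms. The F gate does not help there, because the effective arm opens it. The primary objective consists of these comparisons: glucagon with and without basal reduction, each against basal reduction alone.

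**Working it through.** **1. The plan's own figure.** Noncentrality = N × 59/225. With 14 per arm, 42 × 59/225 = 11.0, and the power is 82.3%; with 13 per arm it is 78.9%. So 14 reproduces, with 59 as the divide-by-three variance of the means. If both glucagon arms share one mean, 2d²/9 = 59, so the gap to control is d = √(59 × 9/2) = 16.3.

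**2. Does a common SD fit that gap?** Assumption: units are % of sessions, which the plan does not state. A proportion with mean p has variance at most p(1−p).
- Control 20%, SD 15: 0.0225/0.16 = 0.14 of the maximum. Glucagon is then 20 − 16.3 = 3.7%, with maximum 0.037 × 0.963 = 0.0356. An SD of 15 there needs 0.0225/0.0356 = 0.63 of the maximum. Holding 0.14 gives SD √(0.14 × 0.0356) ≈ 7, a ratio near 0.47.
- Control 33%: the same steps give a ratio near 0.79.

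The planning values therefore make some inequality plausible, but they do not fix its size.

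**3. Both glucagon SDs equal to r × control SD σ.** Pooled variance = σ²(1+2r²)/3. Squared standard error used = 2σ²(1+2r²)/(3n); correct value = σ²(1+r²)/n. Their quotient is 2(1+2r²)/[3(1+r²)]: 1 at r = 1, 0.80 at r = 0.5, 0.73 at r = 1/3, 0.67 at r = 0.1. As a standard error it is too small by factors of 0.89, 0.86 and 0.82 in the last three cases.

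Simulated coverage of the unadjusted pooled 95% interval, glucagon versus control (normal data, 14 per arm, 200,000 trials):

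| SD ratio r | 1 | 0.75 | 0.5 | 0.33 | 0.25 | 0.1 |
|---|---|---|---|---|---|---|
| Pooled | 95.0% | 93.9% | 91.7% | 90.1% | 89.2% | 88.1% |

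Welch intervals covered 94.9-95.1% throughout. Using 16 per arm changes pooled coverage by at most 0.2 points. With beta-binomial rates over 24-36 sessions (2-3 per week for 12 weeks, Protocol 8.4), assumed control and glucagon rates gave: 33% vs 1%, 88.2%; 20% vs 4%, 89.4%; 33% vs 5%, 90.5%; 20% vs 5% with milder SDs, 91.9%; 20% vs 8% and 12%, 94.6%. Welch gave 93.7-95.3%.

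**4. A different state: one glucagon arm works (SD ratio r, mean 16.3 lower), the other equals control.** Pooled variance = σ²(2+r²)/3. For ineffective arm versus control the quotient is (2+r²)/3 = 0.70 at r = 1/3, so the standard error is too small. For effective arm versus control it is 2(2+r²)/[3(1+r²)] = 1.27, so it is too large, and that interval covers 96.9%. The F gate opens in 97% of trials at r = 1/3. False-positive rate for ineffective arm versus control:

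| r | F-gated unadjusted LSD | Tukey | Welch |
|---|---|---|---|
| 0.5 | 9.0% | 4.4% | 5.0% |
| 0.33 | 9.9% | 5.0% | 4.9% |
| 0.1 | 11.0% | 5.8% | 5.0% |

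Beta-binomial versions gave 8.5-10.6%, 4.0-5.5% and 4.5-5.1%.

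**5. The rate as written.** SAP 4.3.6 and Protocol 12.4.1 divide sessions by events. In simulation that quantity had an SD of 4.5 and 8.4 at event rates of 33% and 20%, and about 10 at 5% and 3%. It was undefined (no events) for 40% and 53% of subjects at the two low rates. The variance pattern reverses, and pooled intervals against control would tend to over-cover.

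**6. The normality gate.** Shapiro-Wilk on pooled residuals rejected 84-100% of strongly unequal beta-binomial datasets. In another set of scenarios 12-39% passed (about 0% in the most extreme), and coverage among those passing was 84-92%.

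**The case against.** A reader might infer that this trial's intervals will cover only 88-91% and that its pairwise error will be 10%. The documents do not support that, for five reasons.

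- No arm-specific SD is given. Low rates on glucagon rest on 0 of 15 in single supervised sessions (exact 95% upper limit 21.8%), not on 12 weeks of self-managed exercise. Coverage of 91% or less needs both glucagon SDs at about 0.4 of control or below.
- The two figures cannot hold together. The coverage loss in step 3 needs both glucagon arms tight; the false-positive rate in step 4 needs one of them to equal control, and then the effective arm's own interval is conservative. The pilot's glucagon condition was an alternative to basal reduction, so it resembled Treatment C. It gives no reason to expect C to equal control while B works.
- The doubling belongs to unadjusted LSD. Appendix 1 is example code, and Tukey on the pooled variance removes most of the excess.
- Most strongly unequal datasets would fail Shapiro-Wilk and leave the ANOVA branch.
- Where the effect is large, a slightly narrow interval rarely changes the conclusion: at 20% versus 4%, gated LSD detects the difference in about 99% of trials.

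These objections limit the size; they do not remove the gap. The ANOVA branch names no pairwise method, and its only interval code is unadjusted and pooled. Leaving that branch is not a remedy either: the non-parametric route does not address unequal variance, specifies no interval, and uses Friedman's test, which is meant for matched or repeated data and not for parallel arms.

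**Conclusion.** The concern holds conditionally. The primary analysis pools one variance over arms that may differ in spread, with no check and no alternative. With the rate taken as events per session, the unadjusted pooled interval for glucagon versus control covers from 95% (equal SDs) to about 88% (ratio 0.1), with about 92% at a ratio of 0.5 and 89-90% at 0.33. In the separate one-arm-works state, F-gated unadjusted LSD gives about 8.5-11% false positives for the ineffective arm, against about 4-6% with Tukey and about 5% with Welch. The SD ratios, event rates and session counts are assumptions. The result also depends on first correcting the inverted rate formula, which is a larger defect in its own right. This is a worthwhile repair to a Phase 2 analysis, not a fault that invalidates the design.

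**What to change.** 1. Correct the rate in SAP 4.3.6 and Protocol 12.4.1 to events divided by sessions.
2. In SAP 4.3.6 and Appendix 1, specify arm-specific variances for the primary comparisons: Welch ANOVA, or PROC MIXED with CLASS trt_o, MODEL param = trt_o / DDFM=SATTERTH, REPEATED / GROUP=trt_o. This is the device already present in Appendix 3.
3. Report Welch-type intervals for each glucagon arm against control, and name the pairwise method, for example Games-Howell.
4. State in advance what is done if an arm has no events, since its estimated variance is then zero.

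The cost is a short SAP amendment and a few code lines. Intervals against control widen when variances are unequal, and power falls by roughly 1-5 points (89% to 84% in one simulated case of 25% versus 8%). With equal variances there is essentially no loss (66.5% versus 66.7%). Moving from unadjusted LSD to an adjusted pairwise method costs some further power that these figures do not include.

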8.5. Measures to Minimize Bias: Randomization and Blinding

The study statistician will create the randomization schedule for the study. The randomization assignment for the participant will be conducted once at the time of enrollment with confirmation of subject eligibility. The CRC assignments will be by random assignment during the first session to either Glucagon RTU or placebo. At the second session, the participant will be crossed over to the other treatment assignment. At the completion of the CRC visits, the subject

will then have the treatment assignment applied for the parallel group study. The randomization schedule methodology for the Outpatient setting is by permuted random block to 1 of 3 treatment assignments in a 1:1:1 ratio.

1. A 50% reduction in basal insulin rate 5 minutes before exercise + pre-exercise injection of placebo (blinded)
2. A 50% reduction in basal insulin rate 5 minutes before exercise + pre-exercise injection of Glucagon RTU (blinded)
3. No reduction in basal insulin rate + pre-exercise injection of Glucagon RTU (open label)

The cross-over study is blinded to the extent possible since all participants will receive both Glucagon RTU and placebo. All staff, participants and study team members will know that the participant will receive both study treatments during the CRC sessions. During the outpatient study, two of the treatments will be blinded to the study staff, participants and Sponsor. One arm of the study will be open-label. It is imperative for the study staff to remain blinded to treatment assignment prior to randomization and during the study treatment periods as not to bias the outcome.

Glucagon RTU and placebo will be prepared and administered so that each will be indistinguishable from the other.

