**Figure 1. Schema of Study Design**

The CRC Stage will involve two daytime clinical research centers (CRC, or comparable setting) exercise sessions 2-28 days apart, in a morning exercise session, for the following treatment assignments:

- Insulin pump reduction (50% reduction in basal rate five minutes before exercise, for the duration of the exercise), and pre-exercise placebo injection (30  $\mu$ L vehicle), or
- Insulin pump reduction (50% reduction in basal rate five minutes before exercise, for the duration of the exercise), and pre-exercise Glucagon RTU (30  $\mu$ L active - 0.15 mg).

At Investigator discretion, the insulin pump rate can be reduced overnight based on subject's medical history for the duration of the study.

BGM assessments during CRC visits will be at -15, 0, 30, 45 and 75 minutes from the start of exercise. Venous Blood Glucose assessments (Yellow Springs Instrument [YSI] readings) during CRC visits will be at -15, 0, 15, 30, 45, 60 and 75 minutes from the start of exercise. Subjects will also wear unblinded continuous glucose monitoring (CGM) both the CRC and Outpatient Stages of the study.

The Outpatient Stage will be 12 weeks in duration during which subjects are randomized to one of three parallel treatment arms, two of which are double-blinded, and one is open-label.

During the Outpatient Stage, subjects will receive one of the following randomly assigned treatments:

- Insulin Pump reduction (50% reduction in basal rate five minutes before exercise, for the duration of the exercise), and pre-exercise placebo injection (30 µL vehicle), or
- Insulin Pump reduction (50% reduction in basal rate five minutes before exercise, for the duration of the exercise), and pre-exercise Glucagon RTU (30 µL active - 0.15 mg), or
- Pre-exercise Glucagon RTU (30 µL active - 0.15 mg) without pump changes.

Subjects will measure blood glucose using BGM at -15 and 0 minutes (just before exercise) to establish baseline, at 30 minutes of exercise, at the end of exercise, and 30 minutes post-exercise. Subjects will also wear unblinded CGM during the conduct of the study.

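### The primary ANOVA is valid, but it leaves unused a likely prognostic measure the trial already collects: the glucose response in each subject's CRC placebo session

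*SAP*

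**What the plan says.** **Primary model.** SAP 4.3.6: "The primary efficacy analysis will be analyzed by ANOVA comparing the mean incidence rate between the three treatment groups". All three example programs in SAP Appendix 1 have outpatient treatment as the only term ("MODEL param = trt_o"). Protocol 12.4.2 also specifies an ANOVA across the three groups and names no covariate.

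**What is collected beforehand.** In the CRC Phase each subject crosses over between Glucagon RTU and placebo, both with a 50% basal reduction (Protocol 6.1; SAP 1.2). The placebo condition is worded the same as the outpatient control arm. SAP 1.2: "Venous Blood Glucose assessments (Yellow Springs Instrument [YSI] readings) during CRC visits will be at -15, 0, 15, 30, 45, 60 and 75 minutes".

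**Timing.** There is one randomization, at Visit 3 (Protocol 10.3.1). The outpatient schedule uses "permuted random block to 1 of 3 treatment assignments in a 1:1:1 ratio", and the outpatient assignment is applied only once the CRC visits are complete (Protocol 8.5; SAP 1.3.1).

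**Adjustment elsewhere.** SAP 4.3.7 analyses questionnaire changes by ANCOVA that includes the baseline value. The general model for incidence rates in SAP 4.3.8, in the exploratory section, allows sex, age, weight and sequence. Neither document uses the CRC glucose response as a covariate for the primary endpoint.

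**The concern.** People with type 1 diabetes may well differ in how far their glucose falls during exercise. If a subject's fall under the control regimen predicts his or her later rate of exercise hypoglycemia, a treatment-only model leaves that variation in the error term. With about 14 subjects per arm, the model also leaves chance imbalance on that trait uncorrected. The usual reason for not adjusting is that nothing suitable was measured. Here a candidate is measured, and the SAP already adjusts its questionnaires for baseline. Precision in the primary comparison is at stake, not its validity.

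**Working it through.** **1. Reproduce the plan's figure.** SAP 1.3 gives the inputs: "With an effect size estimate of 0.262 (variance of means 59, common standard deviation 15), 80% power and an alpha of 0.05". From these it arrives at 14 per arm, by a one-way ANOVA.

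- f² = 59 / 15² = 59/225 = 0.262, so the stated effect size is f².
- Noncentrality λ = 3n × 59/225, with df = (2, 3n − 3).
- n = 13 per arm gives 78.9%. n = 14 gives λ = 42 × 59/225 = 11.01 and 82.3%. The stated 14 per arm is reproduced.

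**2. Add one covariate.** Let ρ be the within-arm correlation between the CRC placebo-session glucose fall and the outpatient rate. The documents give no value, so ρ is an assumption. Residual variance is multiplied by 1 − ρ², so λ = 11.01 / (1 − ρ²), with df = (2, 38). For example, ρ = 0.3 gives 11.01/0.91 = 12.10, and ρ = 0.5 gives 11.01/0.75 = 14.68.

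The formula treats the covariate as balanced across arms. The simulation does not: it draws the covariate at random (200,000 trials per ρ, 14 per arm, SD 15). It sets the control mean above two equal active means by √(59 × 9/2) = 16.29, which gives a variance of means of 59. The simulation is the fairer guide.

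| ρ, same in all arms | ANCOVA, formula | ANCOVA, simulation |
|---|---|---|
| 0 | 82.2% | 81.3% |
| 0.2 | 83.8% | 82.8% |
| 0.3 | 85.8% | 84.9% |
| 0.4 | 88.6% | 87.8% |
| 0.5 | 92.0% | 91.2% |

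The comparator is 82.3% unadjusted. Break-even is at ρ of about 0.05 by formula and about 0.15 to 0.2 in simulation.

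**3. Let the correlation differ by arm.** Two of the three outpatient arms inject glucagon, which may weaken the link with a placebo-session response.

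| ρ control | ρ glucagon arms | ANCOVA, simulation |
|---|---|---|
| 0.5 | 0.25 | about 86.6% |
| 0.5 | 0 | about 83.1% |
| 0.3 | 0 | about 82% |

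**4. Chance imbalance.** With 14 per arm, the difference between two arm means of a covariate has standard error √(2/14) = 0.378 SD. A gap of more than half an SD is 0.5/0.378 = 1.32 standard errors, which arises about 19% of the time (two-sided, normal approximation).

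**5. The form of the covariate matters.** Outpatient exposure is 2 to 3 sessions a week for 12 weeks, or 24 to 36 sessions. A yes/no hypoglycemia result from one CRC session would carry an assumed ρ of only about 0.15 to 0.3 with a rate over that many sessions, a gain of about 0 to 3 points. A continuous glucose fall could do better. It is, however, tied to the starting value. Sessions start between 100 and 180 mg/dL and stop with glucose tablets at 70 mg/dL or below (Protocol 10.3.1, Appendix 1). A subject starting at 100 is stopped after a fall of 100 − 70 = 30, while one starting at 180 reaches the threshold only after 180 − 70 = 110. The fall should be measured up to rescue and the starting glucose included in the model.

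**The case against.** The strongest reply is that nothing here is an error. The unadjusted ANOVA is valid, it is the model on which the trial was sized, and it meets its 80% target. That stands. A reader might infer that the primary analysis is biased or underpowered, and the documents do not support that.

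A second tempting reading is that power rises to 92% at no cost. That figure comes from the formula and needs ρ = 0.5 in every arm. In the pilot described in Protocol 4.2, 5 of 15 subjects had hypoglycemia with insulin reduction and none with Glucagon RTU. Those are single sessions in a small sample. Still, if glucagon-arm rates are near zero, a placebo response has little there to explain, and step 3 shows the gain almost vanishing. An uninformative covariate costs about 1 point.

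A third is that every subject supplies a true baseline of the control-arm outcome. This goes too far in several ways:

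- The session follows randomization and falls in period 1 or 2 according to sequence.
- It is one fasted, supervised, 45-minute morning session measured by YSI. The outcome is a BGM-defined rate over 12 weeks of sessions lasting 30 to 75 minutes at any time of day.
- Starting glucose may first be moved by dextrose tablets or IV insulin.
- A randomized subject who leaves between the CRC visits may lack the placebo session.

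These points limit how prognostic the measure can be and how it must be modelled. They do not make it invalid. Outpatient treatment has not begun, so it cannot have altered the response. What must be ensured is that the outpatient allocation, which includes an open-label arm, stays concealed until the CRC visits end.

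**Conclusion.** The point holds as a recommended efficiency gain, not as a defect. If the covariate is moderately prognostic in all arms (ρ 0.3 to 0.5), power rises by roughly 3 to 9 points in simulation. If it is prognostic in the control arm only, the gain is about 1 point or none. If it is uninformative, about 1 point is lost, and slightly more with the added terms. The benefit is therefore uncertain and the possible loss is small.

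These figures rest on the plan's effect size and SD, 42 evaluable subjects, approximately normal rates with equal variances, an assumed ρ, and the glucose-fall covariate alone. They also presuppose a usable outcome. SAP 4.3.6 and Protocol 12.4.1 both define the rate as sessions divided by events, which is inverted and undefined for a subject with no events. Neither model delivers the stated power on that variable.

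**What to change.** Amend SAP 4.3.6 and Appendix 1 before unblinding:

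- **Outcome:** incidence rate = hypoglycemic events divided by exercise sessions, per subject.
- **Primary model:** ANCOVA with outpatient treatment, CRC placebo-session glucose fall, that session's starting glucose, and CRC sequence. Starting glucose is the mean of the −15 and 0 minute YSI values. The fall is that mean minus the lowest YSI value from 15 to 75 minutes, using values up to any rescue.
- **Missing covariate:** use the overall mean, so that no subject with an outpatient rate is lost. State this as an explicit exception to the no-imputation rule in SAP 2.2.
- **Non-parametric path:** rank ANCOVA (Quade) if it is triggered.
- **Sensitivity analysis:** the unadjusted one-way ANOVA.
- **Concealment:** state that the outpatient allocation is not revealed until the CRC visits are complete.

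The cost is SAP wording and three model degrees of freedom (error df from 42 − 3 = 39 to 42 − 6 = 36 at 14 per arm). No new data or visits are needed.

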4.2. Background

In Protocol No. XSMP-201, a Phase 2a clinical trial, Glucagon RTU was evaluated in a dose-seeking study among 12 adults aged 18 to 50 years with T1D. The study was conducted in an inpatient clinical research center setting, and tested doses of 75, 150, and 300 µg. Subjects were

studied on 3 separate occasions using 2 independent injections of glucagon on each study day. All treatments were well tolerated, no SAEs were observed and AEs were generally mild in nature and consisted primarily of pain or a burning sensation at the injection site. Observations of edema and erythema were generally mild and transient. Nausea occurred at the high dose only, in one- third of the patients.

Glucagon injections were made both after an overnight fast and several hours later, following an injection of insulin to mimic the amount they would have taken for a 30-g carbohydrate snack. The study results showed a clear dose response with an initial response observed after 15 to 20 minutes, and the peak time of response after 30 to 45 minutes, both after an overnight fast and following insulin to induce mild hypoglycemia. In all cases, subjects responded to the 150 and 300 µg doses with an increase of plasma glucose of 40 to 100 mg/dL following an overnight fast, and a somewhat smaller increase of 40 to 60 mg/dL following insulin. The 75 µg dose resulted in a smaller rise in glucose (+30 mg/dL) in most subjects, but in no case did the glucose continue to decrease after SC glucagon administration even at that lowest dose. On the basis of these results, a dose of 150 micrograms was selected for a follow-up study for prevention of exercise-induced hypoglycemia.

Protocol No. XSMP-203 was a single-blind, randomized 4-way crossover pilot study involving 15 adult subjects with T1D, ages 18 to 64 years, using continuous subcutaneous insulin infusion (CSII) and wearing a continuous glucose monitor. At 5 minutes prior to 45-minute sessions of moderate aerobic exercise, subjects received a 150-µg dose of Glucagon RTU or performed one of 3 alternate approaches for prevention of hypoglycemia: (1) consumed 20-gm glucose tablets, (2) implemented a 50% reduction in basal rate insulin, or (3) no intervention prior to exercise (ie, untreated control).

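### SAP 4.3.6 makes Friedman's test the non-parametric fallback for the primary endpoint, but three independent parallel arms supply no blocks for it, and every pairwise test in that branch waits on its result

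*SAP*

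**What the plan says.** SAP 4.3.6 compares the mean per-subject incidence rate across the three Outpatient groups by ANOVA, with post-hoc comparisons if the F-test gives p<0.05. It then adds a fallback: "Parameters that do not meet normality criterion will be analyzed non-parametrically". The overall test in that fallback is fixed: "Overall treatment effect will be assessed using Friedman's test". The next step depends on it: "If the overall treatment effect is significant in the Friedman's test, pairwise treatment comparisons will be assessed using the following tests".

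Two pairwise options follow. One is a Tukey test if the difference between two treatments is normally distributed. The other is a sign test or Kruskal-Wallis test, introduced by "If the difference between two treatments is not normally distributed and the distribution is highly skewed".

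On design, SAP 1.2 says that in the Outpatient Stage "subjects are randomized to one of three parallel treatment arms". Protocol 8.5 says allocation is "by permuted random block to 1 of 3 treatment assignments in a 1:1:1 ratio". It gives no block size, and the SAP does not carry the blocks into any analysis.

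Elsewhere, SAP 4.3.7 and 4.3.8 use Kruskal-Wallis in place of ANOVA for non-normal time and proportional-time measures, and Appendix 2 has its code. Appendix 1 has ANOVA-type code and a Shapiro-Wilk check on residuals. Protocol 12.4.2 names only ANOVA with post-hoc comparisons.

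**The concern.** Friedman's test is for complete blocks, such as subjects who each receive every treatment. In the Outpatient Stage each subject has one treatment and one rate. The condition on a difference between two treatments, and the sign test, also presuppose pairs, and there are none between independent arms. Kruskal-Wallis, which would fit, appears in 4.3.6 only as a pairwise option behind the Friedman result.

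At stake are the overall primary test and both glucagon-versus-placebo comparisons whenever normality fails. The statistician would then have to invent a blocking rule, drop subjects or substitute another test. Any of these could be decided with the data in view.

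**Working it through.** **1. The plan's own sample size.** Inputs from SAP 1.3: variance of means 59, SD 15, two-sided alpha 0.05, three groups. f² = 59/15² = 59/225 = 0.262. With 14 per arm, the noncentrality is 42 × 0.2622 = 11.0 on 2 and 39 degrees of freedom, and power is 82.3%. With 13 per arm it is 79.0%. The stated 14 per arm reproduces.

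For the simulations, the planned effect is taken as one arm a distance d above two equal arms. Then 2d²/9 = 59, so d = √(59 × 9/2) = 16.3 points.

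**2. Subject as block.** For k treatments and n complete blocks, Q = 12/[nk(k+1)] × ΣRⱼ² − 3n(k+1), where Rⱼ is the sum of within-block ranks for treatment j. With k = 3 and the subject as block, each block holds one value. There is nothing to rank.

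**3. Unequal arms.** Q needs the same n for each treatment. SAP 2.2 rules out imputation, and SAP 1.3 expects 15% attrition. If 16 are randomized per arm and each subject independently fails to give a rate with probability q, the chance of three equal arms is Σₓ[C(16,x)(1−q)ˣ q¹⁶⁻ˣ]³:

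| q | Chance of equal arms |
|---|---|
| 5% | 13.9% |
| 10% | 6.6% |
| 15% | 4.5% |

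A subject who leaves late may still supply a rate, so q may be below 15%. Equal arms remain unlikely at all three values.

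**4. Equal arms, arbitrary triplets.** Simulated with 14 per arm:

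- Type I error with normal data: 4.6% (Kruskal-Wallis 4.7%).
- Power at the planned effect with normal data: Friedman 65-66%, Kruskal-Wallis 79-80%, F-test 82%.
- Power with beta-binomial rates, SD 15 and glucagon arms at 20-30%: Friedman 67-71%, Kruskal-Wallis 79-84%. Further runs gave 67-72% against 80-85%.
- The gap narrows at low glucagon rates: 86-87% against 94-95% at 10%, and about 99% against nearly 100% at 5%.
- Row order: six normal datasets, picked for a Kruskal-Wallis p between 0.005 and 0.05, were each re-paired 10,000 times. Within a dataset, the smallest Friedman p was about 0.0001-0.0006 and the largest 0.26-0.81. The share below 0.05 ranged over datasets from 36% to 79%.
- Among beta-binomial trials that reach the branch at the planned effect, 200 re-pairings gave both p<0.05 and p≥0.05 from the same data in 77-86% of trials.

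**5. How often the branch is reached.** Assumptions: the rate is events per session, outcomes are beta-binomial, and the trigger is Shapiro-Wilk p<0.05 on ANOVA residuals with 14 per arm. Protocol Appendix 1 asks for 2-3 sessions weekly, so 24-36 sessions over 12 weeks; 12-24 was also tried in case fewer qualify.

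| Placebo / glucagon / glucagon rate | Branch reached |
|---|---|
| 50 / 34 / 34%, SD 15 | 6-7% |
| 40 / 24 / 24%, SD 15 | 19-23% |
| 33 / 17 / 17%, SD 15 | 50-59% |
| 33 / 10 / 10%, within-subject correlation 0.1-0.2 | 61-88% |
| 33 / 5 / 5%, within-subject correlation 0.1-0.2 | 92-99% |

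The 33% comes from the pilot in Protocol 4.2, a "single-blind, randomized 4-way crossover pilot study involving 15 adult subjects with T1D". Hypoglycemia occurred in "5 subjects in the insulin reduction arm, and no subjects using glucose tablets or Glucagon RTU". That is 5/15 = 33% (exact 95% interval 12-62%) for insulin reduction and 0/15 (upper limit 22%) for Glucagon RTU.

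**The case against.** A reader might infer that Friedman's test can give no valid result here. That goes too far: triplets formed without regard to outcome hold the 5% level. The faults are that no block is defined, the answer is not unique and power is lost. The 77-86% figure likewise shows non-uniqueness over many re-pairings, not how often one programmed run would mislead.

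A reader might also infer that the software must fail. The error was seen in scipy with arms of 14, 13 and 15, whereas SAP 2 specifies SAS 9.3 or higher. The general rank-score (Cochran-Mantel-Haenszel) form accepts unequal arms, and with a single stratum it equals Kruskal-Wallis. The SAP does not specify that form, so the ambiguity stands.

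The randomization blocks could be proposed as the missing blocks. With an assumed size of 3 and 15% loss, 0.85³ = 61% stay complete, so 16 × 0.614 = 9.8 blocks (29 of 48 subjects) remain, and Friedman power is 48-52%. That is a worst case. Keeping partial blocks gives 56-64% and blocks of 6 give 66-75%, against 78-85% for Kruskal-Wallis. The documents state neither a block size nor such an analysis.

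The paired wording could be meant for the CRC crossover, where hypoglycemia incidence is also analysed (SAP Table 14.2.4.1.1). But 4.3.6 states the three-arm Outpatient hypothesis, and with two CRC treatments an overall test followed by pairwise tests has no purpose.

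Finally, this is a conditional fallback in a Phase 2 study of preliminary efficacy, and the lead ANOVA is sound. That limits the reach of the fault but does not remove it. The missing Friedman code in Appendix 1 is weak evidence either way, since that code is only an example.

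**Conclusion.** The concern holds for the non-normal branch of SAP 4.3.6 only. The overall test named there does not fit one rate per subject in three independent arms, no block is defined, and all pairwise comparisons in the branch depend on it. Nothing elsewhere in the documents repairs this.

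For equal arms and arbitrary triplets, the cost at 14 per arm and the planned effect is a fall in power from about 79-85% to about 65-72%, and a p-value that row order can move across 0.05. For unequal arms, which are the likely case, the complete-block test cannot be run on all subjects.

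The misfit follows from the text and needs no assumptions. The frequency does: about 7% to 57% at the planned effect for placebo rates from 50% down to 33%, and higher if glucagon-arm rates are lower. Those figures take the rate as events per session. SAP 4.3.6 literally divides sessions by events, which leaves subjects with no events without a value. The pilot rate comes from 15 subjects in single sessions and is a weak guide to 12 weeks of outpatient exercise.

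The documents do not support extending the point to the ANOVA, to the sample size or to an inflated type I error.

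**What to change.** In SAP 4.3.6, before unblinding:

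1. Replace Friedman's test with Kruskal-Wallis as the overall three-arm fallback, as 4.3.7 and 4.3.8 do for time and proportional-time measures.
2. If it is significant, compare arms by one named rank method for independent groups. Wilcoxon rank-sum tests after the gate control family-wise error with three arms: if all arms are equal the gate protects, and if one arm differs at most one true null remains. Dwass-Steel-Critchlow-Fligner or Holm are more conservative alternatives.
3. Remove the paired-difference check and the sign test from the Outpatient analysis. They may stay for the CRC crossover.
4. As a minor clarification, state the trigger as Shapiro-Wilk p<0.05 on the ANOVA residuals.

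The cost is SAP wording, with no added subjects and the code already in Appendix 2. In simulation, the gate with unadjusted rank-sum tests gave any false rejection in 4.5-4.9% of trials with no effect, and rejected the one true-null pair in 4.5-5.3% at the planned effect. Power for each glucagon-versus-placebo comparison was 70-77%, or 60-68% with Holm or Dwass-Steel-Critchlow-Fligner after the gate.
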